9.5.13. Treatment-Emergent AEs and AE Duration

Only treatment-emergent AESIs and SAEs, will be summarized, unless otherwise stated. A treatment-emergent AE is an AE that emerges on or after the first treatment dose, having been absent pre-treatment, or that worsens relative to the pre-treatment state.

The duration of the AE will be calculated as follows:

Duration of AE (days) = Date of AE resolution – AE start date + 1.

If the AE is ongoing the duration will be left blank and no imputation will be done.

9.5.14. Incidence Rate

Event incidence rates and subject incidence rates will be calculated for Mortality and Malignancy and other AESIs during the on-treatment and on-study (to Week 52) periods as defined below. Note, for Mortality only subject incidence rates will be calculated. Subject incidence rates will also be calculated for SAEs during the on-treatment and on-study periods at the SOC level only.

Typically for subject incidence rates the subject years would be censored at the time of the event for subjects who experience the event i.e. the subject years contributed to the incidence rate calculation for a subject would be the total years from treatment start date to the event date. However, in consideration of the low number of events, this additional adjustment is not anticipated to have a significant impact. Therefore, the additional adjustment will not be used and the subject years contributed by a subject with an event will be the total years from treatment start date to the end of the treatment period of interest for all AESIs and mortality.

On-treatment

$$\text{Subject Incidence Rate} = 100 \times \frac{\text{Number of Subjects with an Event}}{\text{Overall Subject Years On – Treatment}}$$

$$\text{Event Incidence Rate} = 100 \times \frac{\text{Number of Events}}{\text{Overall Subject Years On – Treatment}}$$

Where overall subject years of on-treatment follow-up =

$$\sum_{\text{all subjects in population}} [\text{on-treatment follow-up in years}]$$

See Section 9.5.4 for detail on the calculation of on-treatment follow-up.

On-study (to Week 52)

$$\text{Subject Incidence Rate} = 100 \times \frac{\text{Number of Subjects with an Event}}{\text{Overall Subject Years On – Study}}$$

$$\text{Event Incidence Rate} = 100 \times \frac{\text{Number of Events}}{\text{Overall Subject Years On – Study}}$$

Where overall subject years on-study =

$$\sum_{\text{all subjects in population}} [\text{on-study follow-up in years}]$$

See Section 9.5.4 for detail on the calculation of on-study follow-up.

As described in Section 9.1.1, the on-study follow-up (to Week 52) will be different for Mortality and Malignancy compared with other AESIs. This is expected because subjects who withdraw from the study may re-consent to be followed up at Week 52 where only mortality and malignancy data are collected.

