5.6.2.8. Subject Years Follow-Up: Malignancy Subject Incidence Rate

In order to calculate the follow-up adjusted subject incidence rate of new malignancies per 100 subject years by follow-up year (cumulative), the subject years follow up will need to be defined for each subject at each follow-up time point.

This will be done in a similar way to subject years follow-up for mortality (Section 5.6.2.6) but will use date of follow-up contact, rather than date last known alive, as the censoring date. And will use date of diagnosis, rather than date of death as the event date (note: date of diagnosis using SDTM.CE.CESTDTC).

Note: New malignancies reported at Week 52 with a diagnosis of 'UNKNOWN,NO FOLLOW-UP' (SDTM.CE.CETERM) will not be considered to be malignancies (see Section 5.6.2.5).

For each subject a single date of first new malignancy or last follow-up contact date will be derived as follows.

For subjects who entered the follow-up period (i.e. are in any of the Year 2 to 5 population subsets):

- For subjects who have a new malignancy reported, the date of diagnosis of the first new malignancy will be used in the subject follow-up years calculations. Note: this includes malignancies reported by Week 52.
- For subjects who have not reported a new malignancy at any follow-up visit, the date of last follow-up contact across all follow-up visits will be found (using all visits where the new malignancy question was answered as NO) and used as the censoring date. If this follow-up contact date is later than the last known alive date (or date of death) used in the mortality subject years follow-up then the date of last known alive (or date of death) will be used as the censoring date instead.
- For subjects where the date of last follow-up contact across all follow-up visits is missing (i.e. subjects who have not reported a new malignancy and have no Year 2-5 follow-up visits where the new malignancy question was answered as NO), then the study completion or withdrawal date from the Week 52 double-blind treatment period will be used as the censoring date. In calculations, the data for these subjects will be truncated so that subject follow-up years does not exceed 365 days for these subjects.

For subjects who did not enter the follow-up period (i.e. are not in any of the Year 2 to 5 population subsets):

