3. STUDY DESIGN

This is a global, multi-center, randomized, double-blind, placebo-controlled, 52-week study to assess mortality and AESI in adults with active, autoantibody-positive SLE treated with belimumab plus standard therapy vs placebo plus standard therapy. Approximately 4,000 subjects will be randomized (1:1) to belimumab plus standard therapy or placebo plus standard therapy. Randomization will be stratified for region (US/Canada vs Central America/South America/Mexico vs Europe/Australia/Israel vs Asia; see [Appendix 1: Countries by Region](#) for details of countries and regions), Safety of Estrogen in Lupus National Assessment Systemic Lupus Erythematosus Disease Activity Index (SELENA SLEDAI) score (≤ 9 vs ≥ 10), and steroid dose (≤ 7.5 mg/day vs >7.5 mg/day prednisone or equivalent). There is no minimum score required for the SELENA SLEDAI to be eligible for this study.

Subjects will receive investigational product (IP) on Days 0, 14, 28, and every 28 days thereafter through Week 48 with a final in clinic visit conducted at Week 52. Subjects who discontinue treatment at any time during the study but do not withdraw from study visits will be followed at 28-day intervals through Week 52. If the subject withdraws from study visits prior to Week 52, an attempt will be made to assess mortality and occurrence of malignancy (including NMSC) at Week 52 and annually for Years 2 through 5. See protocol Section 3.1 for further details. If a subject is not contactable (withdrew consent or lost to follow-up), where allowed by individual subject's legal consent status and individual country regulations, sites may utilize other available records to perform a mortality assessment at Week 52 - this may include search of public records aided by an independent party.

An Independent Data Monitoring Committee (IDMC) will review unblinded safety data until the data are locked and analyzed. The IDMC will monitor all SAEs (including all-cause mortality), serious infections, opportunistic infections and other infections of interest, malignancies (including NMSC), selected serious psychiatric events, suicidality and serious infusion and hypersensitivity reactions. Details of the summaries provided to the IDMC by an Independent Statistical Data Analysis Center (SDAC) are described in the IDMC Charter and IDMC Report Template.

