9.1.1. Treatment Period (to Week 52)

Subjects will receive IP through Week 48 with a final treatment period in clinic visit conducted at Week 52. Subjects who discontinue IP prior to Week 48 will have a follow-up in clinic visit performed approximately 4 weeks after the last dose of IP.

Per protocol, subjects may withdraw from IP during Year 1 and continue on study, or may withdraw from Year 1 study visits and consent to a Week 52 follow up. As a result, the time ‘on treatment’ versus the time ‘on study’ will differ for some subjects. Therefore, 2 analysis periods have been defined as the ‘On-Treatment’ and ‘On-Study’ periods. Further detail below.

The primary analysis summaries of Mortality, AESIs and SAEs will be performed using the ‘On-Treatment’ Period (defined in the table below).

Supportive summaries of the primary analysis will be performed using the ‘On-Study’ Period (includes on and off treatment data to Week 52).

For subjects who withdraw and re consent for a Week 52 assessment only mortality and malignancy are assessed at Week 52, whereas all other endpoints will be assessed only up until the time of withdrawal. Therefore, in this case follow-up for mortality and malignancy will be longer than for other assessments.

Study Period	Definition
Pre-Treatment	Date < Study Treatment Start Date
On-Study to Week 52	
All data except Mortality and Malignancy events:
 
Study Treatment Start Date ≤ Date ≤ minimum (Date of Death, maximum (Study Withdrawal or Completion Date (DSSTDT), Study Treatment Stop Date + 28 Days))
 
Mortality and all Malignancy events including NMSC (see Section 9.5.12 for definitions of mortality and malignancy events):
 
 • Alive or Lost to Follow Up at Week 52 Follow-Up: Study Treatment Start Date ≤ Date ≤ minimum (Last Known to be Alive Date, Study Treatment Start date + 371) • Dead at Week 52 Follow-Up: Study Treatment Start Date ≤ Date ≤ Date of Death • Week 52 follow-up missing: Study Treatment Start Date ≤ Date ≤ minimum (Date of Death, maximum (Study Withdrawal or Completion Date (DSSTDT), Study Treatment Stop Date + 28 Days)) 
Note: If the derived on-treatment period (i.e. study treatment stop date + 28 days) ends later than the derived on-study to Week 52 period, the derived on-study period will be updated such that it ends in line with the derived on-treatment period.

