On-Treatment	
All data:
 
 • Study Treatment Start Date ≤ Date ≤ minimum (Date of Death, Study Treatment Stop Date + 28 days)

Note: After study withdrawal or last exposure plus 28 days (whichever occurs later) if AESIs and SAEs are recorded, other than mortality and malignancy, these will not be included in the on-study period. See Section 11.2.1 for further detail on how these events will be handled.

Note: For mortality, date of death will be derived as the end date of the SAE with fatal outcome.

Note: Each study treatment infusion should have a start date and end date recorded, but in some cases only one variable is completed. The study treatment stop date is the date of the final study treatment infusion (taken as the first non-missing date of the final study treatment infusion start or end date).

Note: Only dates will be used to identify start and end of treatment (times will not be considered).

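### Week 52 subject incidence rates keep person-time after the first non-fatal event, and on-study malignancy time can outrun malignancy assessment; both bias supplemental rates slightly low

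*SAP*

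**What the plan says.** The SAP file holds two plans: the Week 52 RAP and the RAP for Years 2 to 5.

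**Week 52 RAP.** Section 9.5.14 acknowledges that subject-years would usually stop at the event. It sets this aside because "in consideration of the low number of events, this additional adjustment is not anticipated to have a significant impact", and concludes that "the additional adjustment will not be used and the subject years contributed by a subject with an event will be the total years" up to the end of the period being analysed. The sentence names all AESIs and also mortality. The same section gives subject rates for SAEs by system organ class.

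Section 9.1.1 defines the periods. On-treatment time, which carries the primary interest, ends at "minimum (Date of Death, Study Treatment Stop Date + 28 days". On-study time for mortality and malignancy together, in subjects alive or lost to follow-up at Week 52, ends at "minimum (Last Known to be Alive Date, Study Treatment Start date + 371", which is Day 372. In subjects who died it ends at death. Section 3 adds that for subjects who cannot be contacted, and where consent and local rules allow, "sites may utilize other available records to perform a mortality assessment at Week 52". Section 9.4.2 likewise describes third-party searches of public sources for mortality information.

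**Years 2 to 5 RAP.** For subjects who report a malignancy, Section 5.6.2.8 says "the date of diagnosis of the first new malignancy will be used in the subject follow-up years calculations", including malignancies reported by Week 52. For the rest, the method "will use date of follow-up contact, rather than date last known alive, as the censoring date". The row for Week 52 is capped at 365 days.

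Section 11.1.1 of the Week 52 RAP makes the difference in percentages the primary assessment and calls the incidence rates supplemental.

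**The concern.** A subject incidence rate counts each subject once, so a subject with an event is no longer at risk of being counted again. Leaving that later time in the denominator can only lower the rate, and it lowers it more in the arm with more events. The plan's reason, few events, suits malignancy but is weaker for serious infections, which Table 1-3 of the protocol puts at 5%.

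The malignancy window raises a separate issue. A records search can show that a withdrawn subject is alive without showing whether a malignancy was diagnosed. Using the last known alive date then adds time during which a malignancy would not have been captured.

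At stake is the accuracy of displayed safety rates. Section 11.1 plans a dot plot of exposure-adjusted on-treatment rates and their differences for mortality and all AESIs. The Years 2 to 5 report will also show a cumulative malignancy rate at Week 52, built on different denominator rules.

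**Working it through.** **1. The plan's own figure.** Section 5.1 gives a 95% CI half-width of ±0.46% for the mortality difference. With half-width = 1.96 × √(2p(1−p)/n per arm):
- p = 0.68%, n = 2,500: 0.456%
- p = 0.564%, n = 2,000: 0.464%

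Both round to 0.46%. The figure concerns a difference in percentages, so no person-time rule affects it.

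**2. Mortality.** Under Section 9.1.1 a subject who dies contributes time to death and no further, in both periods. Stopping at the event is therefore already built in and the understatement is zero. The Years 2 to 5 RAP (Section 5.6.2.6) also stops at death.

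**3. Time after the first event.** Let p be the proportion with an event, T the follow-up, and f the mean event time as a fraction of T.
- Rate as planned: 100·np/(nT)
- Rate stopped at first event: 100·np/(nT − npT(1−f))
- Relative understatement: p(1−f)

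Assumptions: n = 2,000 per arm, T = 1 year, f = 0.5 (events spread evenly) or f = 0 (all on the first day, the worst case). The proportions come from protocol Tables 1-2 and 1-3 and Section 1.2 and are used as one-year values. The 31/5,366 covers longer follow-up, so it is generous for one year.

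| Endpoint | p | As planned | f = 0.5 | f = 0 | Understatement |
|---|---|---|---|---|---|
| Malignancy excluding NMSC | 5/2,484 = 0.20% | 0.20 | 0.20 | 0.20 | 0.1–0.2% |
| Malignancy including NMSC | 8/2,484 = 0.32% | 0.32 | 0.32 | 0.32 | 0.2–0.3% |
| Serious hypersensitivity or infusion reaction | 31/5,366 = 0.58% | 0.58 | 0.58 | 0.58 | 0.3–0.6% |
| Serious infections | 5% | 5.00 | 5.13 | 5.26 | 2.5–5.0% |

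Rates are per 100 subject-years. For serious infections there are 100 events; the denominator falls from 2,000 to 1,950 subject-years (f = 0.5) or to 1,900 (f = 0). A constant-hazard calculation, 1 − p/(−ln(1−p)), also gives 2.5% at p = 5%.

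An illustrative 5% against 6% gives a planned rate difference of 1.00. Stopped at first event (f = 0.5), it is 6/0.97 − 5/0.975 = 6.19 − 5.13 = 1.06. The Wald half-width at 5% is 1.96 × √(2 × 0.05/2,000) × 100 = 1.39, so the shift is small beside the uncertainty.

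**4. On-study malignancy time.** Suppose a share w withdraws evenly over the year, and a share s of these is later found alive at Week 52 from mortality-only information. Assessed time per subject is 1 − w/2 years and added time is ws/2, so the inflation is (ws/2)/(1 − w/2). The documents give neither w nor s; the ranges are assumptions.
- w = 5%, s = 25%: 0.00625/0.975 = 0.6%
- w = 10%, s = 50%: 0.025/0.95 = 2.6%
- w = 20%, s = 100%: 0.10/0.90 = 11.1%

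A true rate of 0.45 per 100 subject-years (the program rate in protocol Section 1.2, used here for scale) would appear as 0.447 at the low end and 0.405 at the high end.

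**5. The malignancy rules side by side.**
- *Stopping at diagnosis:* Week 52 RAP no; Years 2 to 5 RAP yes.
- *Event-free subjects:* the Week 52 RAP uses the last known alive date. The Years 2 to 5 RAP uses the last contact with a negative malignancy answer if there is one in Years 2 to 5 (or the last known alive or death date, if earlier), and otherwise the study completion or withdrawal date.
- *Cap:* Day 372 against 365 days; 372/365 = 1.019, up to 1.9% for a subject followed to the cap.
- *Endpoint:* the Week 52 AESIs separate NMSC (Section 9.5.12); the Years 2 to 5 endpoint includes it (Section 2.2).

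**The case against.** The first-event choice is disclosed and reasoned. The rates are supplemental, the primary percentages are untouched, and at two decimals malignancy and serious hypersensitivity do not move. All of that stands, and it limits the point to a cheap improvement. It does not remove the bias for serious infections, where the reason given is weakest, and the plan offers no reason for tying malignancy time to vital status.

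The two reports are also not like for like: NMSC is handled differently, and on-treatment rates have no counterpart in Years 2 to 5. That stands too. A reader might infer that the reports will contradict each other in a known direction, but the documents do not show this. A subject with no malignancy answer at Week 52 and a later contact can gain time under the Years 2 to 5 rule. One assessed at a Week 52 contact after withdrawal can lose it. Nor would copying the Years 2 to 5 rule be a full remedy, because it can discard assessed time.

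A reader might also infer that mortality rates are understated, since Section 9.5.14 names mortality. The period definitions rule this out. Understatement of 5% to 10% from event rates of 10% or more is likewise unsupported. The 8% to 10% in protocol Table 1-2 covers all depression, suicide and self-injury events, whereas the psychiatric AESI counts serious events only, and no figure is given for SAEs by organ class.

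**Conclusion.** The point holds as a minor one. Subject incidence rates for non-fatal AESIs and for SAEs by organ class are biased slightly low: about 2.5% relative, at most 5%, for serious infections at 5%, and under 1% for malignancy and serious hypersensitivity. This rests on one year of follow-up and on the protocol's earlier-trial proportions.

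The malignancy window may matter more, at roughly 0.6% to 11% excess person-time. That range depends wholly on assumed withdrawal and records-only shares, and it concerns only the supportive on-study period, because on-treatment time ends no later than 28 days after the last dose. Mortality and the primary comparison are unaffected; for mortality the only defect is the wording of Section 9.5.14.

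**What to change.** - For subject incidence rates, end each subject's person-time at the first event of that type. Keep full time for event rates.
- For C-SSRS suicidality, which has no adverse-event onset date, use the first visit at which the score exceeds the pre-treatment maximum.
- End on-study malignancy time at the last date malignancy was actually assessed, counting a Week 52 contact at which the malignancy question was answered.
- Use one cap (Day 365 or Day 372) and one censoring rule for the Week 52 malignancy row in both RAPs. Failing that, footnote the differences in denominator and in NMSC handling.
- Remove mortality from the waiver sentence in Section 9.5.14, or state that both periods already end at death.

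The cost is a small amount of reprogramming. Section 9.4.3 says the eCRF does not accept missing or partial AE dates, apart from end dates of ongoing events, so start dates are available. The Week 52 data were unblinded on 2 January 2019 and have been reported (Years 2 to 5 RAP, Section 1). The corrected rates should therefore be supplied as a labelled post-unblinding supplement, not as a replacement.

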9.5.15. Treatment-Emergent C-SSRS

For suicidal ideation, the pre-treatment reference period is the lifetime history, current history and baseline (for further detail refer to the IDSL documentation). For suicidal behavior, the pre-treatment reference period is the lifetime history and baseline (note: suicidal behavior is not re-assessed for the current history time period).

Suicidal ideation and suicidal behavior will be considered as distinct categories and assessed independently of each other. Treatment emergence will be assessed for the on-treatment period and the on-study period.

Suicidal ideation will be assessed using responses to C-SSRS ideation questions (categories 1 to 5) only. Suicidal behavior will be assessed using responses to C-SSRS behavior questions (categories 6 to 10) only.

- **Treatment emergent suicidal ideation** will be assessed using the maximum ideation score pre-treatment, compared to the maximum ideation score post-treatment (on-treatment or on-study as appropriate). If the maximum ideation score worsens relative to the pre-treatment reference period then this will be considered a treatment emergent suicidal ideation. This is derived from responses to suicidal ideation questions (categories 1 to 5).
- **Treatment emergent suicidal behavior** will be assessed using the maximum behavior score pre-treatment, compared to the maximum behavior score post-treatment (on-treatment or on-study as appropriate). If the maximum behavior score worsens relative to the pre-treatment reference period then this will be considered a treatment emergent suicidal behavior. This is derived from responses to suicidal behavior questions (categories 6 to 10).
- **Treatment emergent suicidal ideation or behavior** will be defined as a subject having a treatment emergent suicidal ideation (as defined above) and/or a treatment emergent suicidal behavior (as defined above). This definition is used to assess the protocol defined AESI endpoint of ‘Suicidality (C-SSRS)’ (see Section 9.5.15).

Suicidal Ideation (categories):

1. Wish to be Dead
2. Non-Specific Active Suicidal Thoughts
3. Active Suicidal Ideation with Any Methods (Not Plan) without Intent to Act
4. Active Suicidal Ideation with Some Intent to Act, Without Specific Plan
5. Active Suicidal Ideation with Specific Plan and Intent

Suicidal Behavior (categories):

6. Preparatory Acts or Behavior
7. Aborted Attempt
8. Interrupted Attempt
9. Non-Fatal Actual Suicide Attempt
10. Completed Suicide

A subject must have at least one pre-treatment C-SSRS assessment (screening and/or baseline) and at least one on-treatment C-SSRS assessment (post-baseline) to be included in any assessment of treatment emergent.

